9.6.3. Secondary Analysis - Feasibility

The secondary analyses concerning the feasibility of patient self-management of treatment intake under recommended conditions will be performed on the subgroup of out-patients from the ITT population, i.e. all patients who were considered as eligible for treatment on an out-patient basis and to whom the IMP was dispensed, regardless of whether or not they took the IMP. The endpoints analysed will be as follows:

- Number and proportion of patients who temporarily interrupted treatment;
- Number and proportion of patients who prematurely discontinued treatment;
- Number and proportion of patients who delayed starting treatment;
- Number and proportion of patients who mislaid treatment units;
- Number and proportion of patients who were hospitalised for reasons related to non-compliance.

Confidential Page 51 of 83

For each of the endpoints, the proportion of patients will be presented with the 95% Confidence Interval (CI).

9.6.4. Secondary Analysis - Packaging

Descriptive results will be presented for the questionnaire completed by the patient and/or caregiver at the dispensing visit (Day 0) and at the EoT visit (Day 11) for the patients treated on an out-patient basis (sub-group of out-patients from the ITT population).

9.6.5. Secondary Analysis - PK

The secondary analyses concerning PK will be performed on the sub-group of patients treated in hospital. Concentrations of fexinidazole and its metabolites in whole blood, as well as estimates of PK parameters derived from a population model will be presented. The data will provide confirmation of data from phase-I studies on a larger scale and, in particular, will provide confirmation that data in patients not included in earlier studies (e.g. pregnant or breastfeeding women) are consistent with those in patients in other studies. PK parameters in patients considered to be treatment failures or who experienced intolerance to fexinidazole will be described individually.

9.7. Interim Analyses

No interim analysis is planned for this study.

9.8. Handling of Missing Data and Patients Lost to Follow-up

The endpoints are based on the outcome at 18 months.

For patients who attended the 18-month visit, but who refused the lumbar puncture planned at the visit, the **primary imputation method** will consist in checking for signs or symptoms of HAT. If no signs or symptoms of HAT are present and trypanosomes are negative, and if the outcome was considered as favourable at the last available assessment, the patients will be considered as treatment successes.

If these criteria are not fulfilled, the patients will be considered as treatment failures. The outcome for patients who did not attend the 18-month visit or later will also be considered as a failure, except for patients who fled the region due to armed conflict or natural disaster.

For the analysis at 12 months, if the lumbar puncture at 12 months is missing, data from the last available assessment will be used:

• the outcome at 18 months will be used, if a lumbar puncture was performed at that visit.

Confidential Page 52 of 83

- if a lumbar puncture was performed at 6 months, but not at 18 months, the patient will be considered as a success if the CSF WBC was ≤ 5/µL and lower as compared to prior values, if no trypanosomes were detected and if no HATrelated symptoms were present at 12 months.
- if a lumbar puncture was performed at 6 months and at 18 months, the outcome at 18 months will prevail.

In situations other than those described above and if no lumbar puncture is available after the start of treatment, the patients will be considered as failures.

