Only patients in whom the presence of parasites is confirmed by at least two team members at the investigational centre and approved by the Investigator, will be included in the study, regardless of the findings reported by the mobile teams. For quality control purposes, it is planned to record digital images of the parasitological tests and CSF WBC counts at the time of the initial diagnosis, as well as during follow-up visits.

In the context of the study, a CSF WBC count of $20/\mu L$, as well as the presence of parasites in any body fluid, will be used to stage the disease, in accordance with the WHO guidelines for clinical studies assessing treatments for late-stage HAT (21).

All patients included in the study will receive fexinidazole, regardless of the stage of the disease. Disease staging based on analysis of CSF obtained on lumbar puncture is necessary because the treatments currently available are not the same for early-stage and late-stage HAT and, in the context of the study, it will provide confirmation of the efficacy of fexinidazole against both stages of HAT.

The end-of-treatment assessment of patients will be based on parasitological tests on the blood and/or lymph on Day 11 and at the 3-month, 6-month, 12-month and 18-month visits, in accordance with the WHO guidelines (21). At the 3-month follow-up visit, lumbar puncture will be performed only in patients with clinical signs of relapse. Lumbar puncture will be routinely performed at the 6-, 12- and 18-month follow-up visits, unless the patient explicitly refuses the test.

Confidential Page 20 of 83

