2.2. Study Endpoints

2.2.1. Primary Endpoint - Effectiveness

The primary endpoint for the assessment of effectiveness will be:

 Outcome (success or failure) at 12 months and 18 months after the end of treatment. Success is defined as a cure, according to the criteria adapted from the WHO (21).

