5.6.5. Rescue Treatment

Patients in whom no response is observed on parasitological testing at the EoH visit, as well as patients who show signs of relapse at any time during follow-up, will receive the treatment recommended by the PNLTHA.

If a patient treated on an out-patient basis interrupts treatment with the IMP after Day 4, s/he will be followed up in the usual manner by the investigational centre in order to detect a possible relapse. In this situation, rescue treatment will be the treatment recommended by the PNLTHA.

If a patient treated on an out-patient basis interrupts treatment with the IMP before Day 4, s/he will receive rescue treatment with NECT if s/he has late-stage HAT or with pentamidine if s/he has early-stage HAT.

Rescue treatment for HAT must be recorded in the appropriate section of the CRF and not as concomitant medication.

Probable relapse at the 6-month, 12-month or 18-month follow-up visit is defined as shown below.

Table 1 – Clinical Classification of Patients

Visit	Ideal timing of visit after end of treatment	Favourable outcome	Uncertain outcome	Probable relapse	Proven relapse
24 hours after EoT	24 hours after the End of Treatment (EoT)	 Patient alive with no evidence of trypanosomes in any body fluid (19) 			 Evidence of trypanosome s in any body fluid
3 months	3 months ± 1 week	Patient alive with no evidence of trypanosomes in any body fluid (no lumbar puncture at 3 months unless Investigator suspects relapse)	Any reason prompting the Investigator to request an additional follow-up visit	Neurological signs or symptoms leading to use of rescue treatment	Evidence of trypanosome s in any body fluid
6 months	6 months ± 1 week	• Patient alive with no evidence of trypanosomes in any body fluid and CSF WBC ≤ 20/μL	CSF WBC between 20 and 50/µL and additional visit requested within 1-3 months Any reason prompting the	CSF WBC ≥ 50/µL (24) Neurological signs or symptoms leading to use of rescue treatment	Evidence of trypanosome s in any body fluid

Confidential Page 31 of 83

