**Table 1 : Classification of patients according to stage/severity at inclusion**

Tryps in CSF	WBC in CSF		
	≤ 5/ $\mu$ l	[6-20/ $\mu$ l]	> 20/ $\mu$ l
Tryps in CSF (positive)	Stage 2	Stage 2	Stage 2
No tryps in CSF (negative)	Stage 1	Intermediate stage	Stage 2

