### 6.2. Secondary endpoints

#### 6.2.1. Intermediate endpoint at 12 months

The endpoint for an early assessment of effectiveness will be the outcome (success or failure) at 12 months after the end of treatment. Success is defined as a cure, according to the criteria adapted from the WHO.

The outcome (success or failure) at 12 months will be calculated using the algorithm defined in [Section 10.2](#).

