## 7.6. Handling of missing data and outliers

### Handling of missing data for primary and secondary efficacy endpoints:

Handling of missing data is described in Section 9.8 of the Protocol and is included in the derivation algorithms for outcome at 18 and 12 months (cf. [Section 10](#)).

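### Protocol 9.8 denies Month-12 success to stage 1 patients with stable normal CSF and only a Month-6 puncture, and SAP 10.2 leaves those who are Month-18 successes without a Month-12 outcome

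*Protocol*

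**What the plan says.** **Protocol 9.8** covers the Month-12 analysis when the Month-12 puncture is missing. If a puncture was done at Month 6 but not at Month 18, success needs a count ≤5/µL "and lower as compared to prior values, if no trypanosomes were detected", and no HAT symptoms at Month 12. The section closes with a default for "situations other than those described above and if no lumbar puncture is available after the start of treatment, the patients will be considered as failures".

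**Baseline and earlier counts.** In SAP Table 1, the row beginning "No tryps in CSF (negative" assigns stage 1 to counts ≤5/µL. Baseline is normally the only count before Month 6, because "At the 3-month follow-up visit, lumbar puncture will be performed only in patients with clinical signs of relapse" (protocol, diagnostic process for patients in the study).

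**The protocol's own criterion at 6 months** (Table 1 in 5.6.5) is "Patient alive with no evidence of trypanosomes in any body fluid and CSF WBC" ≤20/µL, with no fall required. At 12 months that table asks for a fall only when the count is between 20 and 50/µL.

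**Status of Month 12.** Protocol 2.2.1 makes it part of the primary endpoint: "Outcome (success or failure) at 12 months and 18 months after the end of treatment". SAP 6.2.1 makes it secondary and says "The outcome (success or failure) at 12 months will be calculated using the algorithm defined in" Section 10.2. SAP 7.6 says that protocol 9.8 "is included in the derivation algorithms for outcome at 18 and 12 months".

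**The concern.** Among patients who start at ≤5/µL, a strict fall between two counts that are both normal does not separate cured from relapsed. The condition does nothing for anyone else: a Month-6 count ≤5/µL is automatically below any baseline above 5/µL. Barring a lower count at an indicated Month-3 puncture, it bites only on patients whose CSF was normal, by cell count, from the start.

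At stake is the Month-12 success rate, chiefly in stage 1. Under the protocol text the rule can only lower it. Under the SAP the same patients have no defined outcome, so someone must choose how to score them after seeing the data.

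**Working it through.** **The plan's own design figure, for scale.** N = 1.96² × 0.87 × 0.13 / 0.05² = 173.8, so 174, as protocol 9.1 states. Clopper-Pearson at 151/174 gives arms of 5.95 and 4.65 points, in line with the stated 6 and 4.5. The point below does not depend on these figures.

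**One patient through each rule.** Take a stage 1 patient with baseline 2/µL and Month-6 count 2/µL, no puncture afterwards, and symptom-free and trypanosome-negative at Months 12 and 18, with no rescue treatment.

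1. Protocol Table 1 at 6 months: favourable (2 ≤ 20).
2. Protocol 9.8 at 12 months: 2 ≤ 5 is met, 2 < 2 is not, so no success.
3. Protocol 9.8 at 18 months, puncture refused: success, if Month 6 is the last available assessment.
4. SAP 10.1, stage 1/intermediate: no Month-12 puncture and no signs at Month 18, so success. The box runs over a page break and is read here with its continuation.
5. SAP 10.2, stage 1/intermediate: there is no count at Month 12 or later and the patient is not a Month-18 failure. The two closing boxes apply only to patients who refused every post-treatment puncture, and this patient had one at Month 6. The column ends without an outcome.
6. SAP 10.2, stage 2, for comparison: a Month-6 count ≤20/µL without signs is a success. There is no ≤5/µL limit and no required fall.

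SAP 10.1 closes both columns with a line for all other cases; SAP 10.2 closes neither with one. SAP Section 11 lists changes to adverse-event counting, interim analyses and an end-of-treatment puncture error, but nothing on this.

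**How often the fall is missed.** From baseline b, only Month-6 counts 0 to b − 1 pass. From 0 none passes; this needs no assumption. Otherwise the share depends on the count distributions, which the documents do not give. Taking both counts as independent and within 0 to 5:

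- Uniform: non-falling pairs = 6 + 5 + 4 + 3 + 2 + 1 = 21 of 36, or 58.3%.
- Same truncated Poisson at both visits, mean 1, 2, 3, 4: 65.4%, 60.7%, 59.7%, 60.4%.
- Month-6 mean below baseline mean (3→2, 2→1, 4→2, 3→1, 4→1): 44.2%, 40.1%, 33.0%, 24.5%, 15.7%.

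**Scale on the Month-12 rate.** Patients = 174 × m × s × f, where m is the share with only a Month-6 puncture, s the stage 1 share and f the share missing the fall. All three are assumed.

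- Low: 174 × 0.02 × 0.30 × 0.25 = 0.3 patients, 0.15 points.
- Middle: 174 × 0.05 × 0.48 × 0.58 = 2.4 patients, 1.4 points.
- High: 174 × 0.10 × 0.60 × 0.80 = 8.4 patients, 4.8 points.

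The 0.48 is the early-or-intermediate share in earlier studies (295/617, protocol 1.4), so it overstates stage 1. Nor does m exclude Month-18 failures. Within stage 1 alone the effect is m × f: 0.5, 2.9 and 8 points.

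**The case against.** The strongest reply is that the protocol clause may never be applied. The Month-12 outcome is computed by SAP 10.2, which contains no such test, and SAP 7.6 says that 9.8 is included in the algorithms, not that it steps in where they are silent. A reader might infer that stage 1 patients with normal CSF will be scored as failures in the analysis; the documents do not support that. This reply stands. What remains is a faulty protocol rule beside a SAP that claims to carry it and instead gives these patients no outcome.

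A reader might also take 9.8 to be the only rule for every stage 1 patient with just a Month-6 puncture. It is not: SAP 10.2 fails at Month 12 anyone with no count at Month 12 or later who is a Month-18 failure for any reason, including loss to follow-up. Removing the fall requirement would not change their result. Only Month-18 successes are left.

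Even under 9.8, failure is partly inferred. The default sentence can be read as one joint condition, and these patients do have a post-treatment puncture. On that reading 9.8 denies them success without stating failure.

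It is tempting to say that around 60% of such patients are misclassified. That needs stable, independent counts; if counts tend to fall after treatment, the share drops to between 16% and 44%.

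Finally, the SAP treats Month 12 as secondary, and protocol 9.5.1 calls Month 18 the more reliable estimate. Both are true and limit the impact. The SAP also cites protocol version 2.0, while the text reviewed is version 3.0, so whether 9.8 read the same in version 2.0 could not be checked.

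**Conclusion.** The point holds in a limited form. For baselines ≤5/µL, the fall required by protocol 9.8 is uninformative, and from 0 it cannot be met. It conflicts with the protocol's 6-month criterion and can deny Month-12 success to a patient whom SAP 10.1 scores a success at Month 18. SAP 10.2 does not apply the rule, has no Month-6 step for stage 1 or intermediate patients, and does not declare the departure.

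The patients concerned are Month-18 successes with a Month-6 puncture and no reliable count at Month 12 or later. Their number is not derivable from the documents and is probably small. The range of 0.15 to 4.8 points rests wholly on assumed inputs, and its upper end is likely too high for the reasons given with the calculation. Only the Month-12 outcome is touched. The repair is worth making because it is cheap and the SAP gap otherwise leaves scoring to a choice made with the data in hand.

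**What to change.** 1. In protocol 9.8, remove the required fall below prior values where the baseline CSF count was ≤5/µL. Keying on the count also covers stage 2 patients with trypanosomes in the CSF but ≤5 cells/µL.
2. In the stage 1/intermediate column of SAP 10.2, add the matching Month-6 step after the box that fails Month-18 failures, and close the column with an explicit outcome for all other cases.
3. Reconcile the ≤5/µL limit in 9.8 with the ≤20/µL limit in the stage 2 column of SAP 10.2 and in protocol Table 1, and reword the ambiguous default sentence in 9.8.
4. List the change in SAP Section 11. That section already records a change after database lock and this one would also come after it, so report the Month-12 rate under both rules, with the number of patients whose outcome differs.

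The cost is one clause and one reworded sentence in the protocol, one step and one closing line in the SAP, a Section 11 entry and one extra table row. No new data are needed.

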9.9. Handling of Centres

The primary analysis will not be stratified by centre because the weight of each centre in the overall population is unknown. Nevertheless, the results by centre will be presented and a test of homogeneity (a likelihood-ratio test) will be performed on the success rates. A centre effect is entirely possible. In this case, an estimate of the overall success rate will also be provided, giving equal weight to each centre rather than weighting the centres based on the number of patients. The estimate of the rate will be given by $p = \sum W_h p_h$ where W_h is the weight of each centre, i.e. the inverse of the number (k) of the centre (k⁻¹). La variance of the estimator will be equal to $Var(P_h) = \sum W_h^2$. $p_h(1-p_h) / n_h$ where n_h is the number of patients in centre h. In addition, a Forest plot will be presented to determine whether the heterogeneity is quantitative (dispersion around a central value) or qualitative (presence of entirely atypical centres).

10. Data and Safety Monitoring Board

A DSMB, composed of at least 3 members independent of the Investigators and the Sponsor, will be set up prior to the start of the study. The DSMB will monitor the study in order to minimise any risk of harm to the patients included in the study. At each of its meetings, the DSMB will examine safety data at predetermined intervals and all information related to SAEs, and will issue recommendations regarding the study if the benefit-to-risk ratio for patients seems to be in jeopardy. The data and the intervals for review will be decided before, or shortly after the start of the study and will be recorded in the DSMB Charter.

The organisation of the DSMB will be described in the DSMB Charter, which will be prepared and approved prior to the first planned meeting.

Additional *ad hoc* members may be invited to join the DSMB if any safety concerns emerge, in order to give additional support to the competencies already present.

11. Quality Assurance and Quality Control Procedures

Confidential Page 53 of 83

11.1. Investigator Site File

The Investigator must maintain appropriate accurate records to ensure that all aspects of study conduct are fully documented, and that study data can be verified at the end of the study. These documents include the Investigator Site File, the patients' clinical source documents, screening/enrolment logs and other study-specific forms.

The Investigator's Site File must contain the protocol and protocol amendments, Independent Ethics Committee (IEC) and regulatory approval with all correspondence, a copy of the patient information and informed consent form, the Investigator Brochure, drug accountability records, Curriculum Vitae (CV) for study personnel, as well as authorisation forms and any other relevant documents or correspondence in accordance with Good Clinical Practice (GCP) and the Sponsor's standard operating procedures.

11.2. Case Report Forms

Data will be collected by laboratory technicians, physicians, nursing staff or care-providers authorised by the Investigator. Data collection will be supervised by the Investigator. Study-specific information will be entered in a CRF in paper format. Data generated from this information must be consistent with the source documents and any discrepancies must be accounted for. All data that are recorded directly in the CRF must be rendered anonymous, i.e. such that they can only be identified by the patient's number.

The Investigator must ensure the accuracy, completeness, legibility and timely entry of all data reported to the Sponsor via the CRF, as well as any additional information that may be requested. The Investigator is responsible for ensuring that all informed consent forms and screening forms for all patients are stored in a secure location. After each visit, data will be entered in the CRF, scanned and sent by Internet to the data manager for entry (double data entry) in the database. The CRF will be signed by the Investigator as the study advances and the CRF pages are sent.

11.3. Source Documents

The data in the CRF must be verified by direct inspection of the source documents. The source documents are the patient's medical files, the physicians' and nursing staff's notes, appointment books, originals of laboratory test results, ECG tracings, reports on specific assessments, signed informed consent forms, recorded images of microscopic examinations and patient screening/enrolment logs. The questionnaires on D0 and D11 on product packaging are also considered as source documents.

Confidential Page 54 of 83

In the study, 100% source document verification will not be carried out. Instead, the focus will be on monitoring for data consistency (cf. the monitoring plan).

The Investigator must keep the source documents up to date, i.e. reports on laboratory tests and consultations, records of medical history and physical examination reports, so that they can be examined and/or audited by the Sponsor / designated clinical monitors and/or by the Regulatory Authorities, if appropriate.

11.4. Retention of Documents

The Investigator must retain all essential documents for at least 25 years after the official stop date of clinical development of the IMP. However, study documents may need to be retained for a longer period of time if required by local regulations in effect or by agreement with the Sponsor. It is the responsibility of the Sponsor to inform the Investigator/institution as to when these documents no longer need to be retained. After that date, the documents may be destroyed with prior permission from the Sponsor, subject to local regulations.

The Sponsor must be notified in advance if the Investigator plans to assign the study records to another party or move them to another location.

11.5. Monitoring

Clinical monitors will perform regular monitoring visits during which they will verify source data, Informed Consent Forms, medical records, laboratory test results, imaging reports, CRFs, drug dispensing logs and protocol violations. The monitors will be given access to the corresponding source documents for each patient on condition that that the patient's confidentiality is maintained in accordance with local regulations.

Monitoring visits at the investigational sites will be performed periodically by representatives of the Sponsor or designated clinical monitors to ensure compliance with Good Clinical Practice and all aspects of the protocol. Source documents will be reviewed for verification of consistency with the data in the CRFs and SAE forms or information provided in response to queries from the Pharmacovigilance Unit at DNDi. The clinical monitor will be responsible for inspecting the CRFs at regular intervals. The Investigator will ensure that the Sponsor's designated representatives have direct access to source documents. It is important that the Investigators and the personnel concerned are available during monitoring visits. The Investigator agrees to cooperate with the clinical monitor to ensure that any problems detected during monitoring visits are resolved.

The monitoring visits provide the Sponsor with the opportunity to assess progress of the study, to verify the accuracy and completeness of the CRFs and to resolve any inconsistencies in the study records, as well as to ensure compliance with all protocol requirements, applicable regulations and Investigator obligations.

Confidential Page 55 of 83

Four types of visit are planned: a site assessment visit, an initiation visit, monitoring visits and a close-out visit.

In addition, data quality will be checked on a regular basis by representatives of the Sponsor in the context of centralised monitoring in order to detect any missing data, inconsistencies, discrepancies and deviations, with analysis of the performance of the investigational centres in order to adapt and/or optimise the monitoring visits and to implement corrective and/or preventive actions, including the need for training, depending on the risks identified and/or deficiencies observed.

